7.5 Safety and Efficacy Assessments/Procedures During Follow-up

The intervention (DBS) in this study is applied for the whole study duration. As such, the safety and efficacy assessments during follow-up visits are the same as what is listed in section 7.4.

Participants will be evaluated biweekly then monthly for the duration of the study (12 months), and then monthly for 3 months after study completion (to evaluate for sustained and clinically meaningful effect) (see Schedule of Research Activities in **Appendix A**).

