3.3 Endpoints

Primary endpoints: safety, tolerability, and feasibility

Safety and tolerability will be evaluated based on adverse events associated with DBS implantation and stimulation (e.g., infection, bleeding, cognitive or behavioral side effects). We will screen for adverse events using 4 approaches: **1)** patient self-report, **2)** clinical evaluations (medical, neurologic, and psychiatric), **3)** questionnaires to screen for depression, anxiety, apathy, and mania, and **4)** neuropsychological evaluation to screen for any LP DBS effects on the various cognitive domains. These will be compared to DBS side effects observed in FDA approved indications like PD.

Feasibility will be evaluated based on **1)** our ability to recruit all 3 patients within the indicated timeframes, **2)** our ability to conduct the necessary evaluations in baseline and follow-up assessments (e.g., alcohol use, PET imaging, cognitive and behavioral tasks) and **3)** patients' adherence to the study protocol and participation in follow-up visits and assessments.

These outcomes will be monitored throughout the entirety of the study (including recruitment, screening procedure, clinical evaluations, DBS implantation, DBS titration, and all other study-related procedures).

Secondary endpoints: alcohol use, overall functioning, and target engagement

Alcohol use: this will be measured by calculating percent days abstinent (PDA), drinks per drinking day (DDD), blood phosphatidylethanol (PEth) and blood gamma-glutamyl transferase (GGT); PDA and DDD are obtained from TimeLine Followback (TLFB) assessment of alcohol use over the past 180 days for baseline evaluation, and over the past 30 days for follow-up evaluations after DBS implantation. PEth and GGT are blood tests obtained at baseline and every month during follow up visits.

Overall functioning and disability: this will be measured using World Health Organization Disability Assessment Schedule 2.0 (WHODAS 2.0) at baseline and during monthly evaluations after DBS implantation.

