 - 3) **Alcohol dependence scale** (ADS-25): 25-item questionnaire that assesses the severity of alcohol dependence based on questions that cover withdrawal symptoms, impaired control, insight into compulsive drinking, tolerance, and drinking related behaviors; usually completed within 5-10 min.
 - 4) **Obsessive Compulsive Drinking Scale** (OCDS): 14-item questionnaire that is sensitive and specific for the obsessive and compulsive aspects of drinking (thoughts, urges, ability to resist the urges); usually completed within 5-10 min.
 - **Overall functioning and disability.** For this assessment, we will use the **World Health Organization Disability Assessment Schedule 2.0** (WHODAS 2.0) questionnaire. This is a 36-question self-administered questionnaire recommended by the DSM-5 to evaluate overall functioning and disability given its high reliability [141]. The questions survey 6 domains related to the participant's wellbeing including cognition, mobility, self-care, getting along, life activities, and participation in society [152].
 - **Mood and anxiety assessments:** these questionnaires aim to screen for any adverse effects of DBS on mood and anxiety.

1) Montgomery Asberg Depression Rating Scale (MADRS): this is a 10-item scale widely used in clinical trials to screen for and assess depression severity. This will be administered weekly over the phone, and monthly during in-person follow up visits. If the phone screening shows a score that is 6 points higher than the previous screening or if it shows severe depression (>35), a study physician will evaluate the participant over the phone and decide if the participant needs to come in for an in-person urgent assessment for further evaluation and risk stratification.

2) Mood and Anxiety Symptom Questionnaire (Mini-MASQ): This is a 26-item scale (~15 min) that assesses 5 subscales of depression and anxiety including anhedonia.

3) Hamilton Anxiety Rating Scale (HARS): this widely used 14-item scale screens for general anxiety.

4) Apathy Evaluation Scale (AES): this is an 18-item scale administered over 10-20 min to screen for apathy by evaluating motivated goal-directed behaviors.

5) Young Mania Rating Scale (YMRS): this is an 11-item scale to screen for manic or hypomanic symptoms. This is usually completed within 5 min.

- **Suicidality:** the Columbia-Suicide Severity Rating Scale (C-SSRS) will be used to assess suicidality to improve safety monitoring.

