DBS Explantation risks: these include hemorrhage and infection but these risks are much lower than during implantation surgery (the risk of infection is low without implanted hardware and the hemorrhage risk is associated with lead insertion, not removal). There is also the possibility of emotional letdown feeling by participants whose DBS was not effective and will be explanted.

Risks associated with DBS titration/optimization include delirium, nausea, memory problems, seizures, mood disorder, mania, hallucinations, suicidal ideation, muscle weakness, shocking sensation, numbness, paresthesias, facial flushing, motor contraction, dizziness, headaches, pain, changes in vital signs, hyperactivity, euphoria, dry mouth, itching, insomnia, fatigue, restlessness, weight gain or loss, speech difficulties, blurred or double vision, unusual smell and taste sensations, and behavioral changes. In addition, it is possible that alcohol use will worsen with DBS stimulation. Specific risks associated with anteromedial GPi DBS targeting include tetanic contraction (posterior limb of internal capsule), photopsia (optic tract), behavioral changes (anterior limb of internal capsule), and behavioral and cognitive changes (substantia innominata).

A review of LP DBS in Tourette's patients [39] reported 7 cases of stimulation-induced side effects that included lethargy, nausea, and paresthesias. However, all these symptoms are reversible with adjustment of stimulation parameters [39].

The device brochure also includes additional warnings about device interactions and precautions (see appendix B).

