12.3 Analysis of Primary Endpoints

The primary outcomes are:

- 1) *Safety and tolerability* measured as incidence of any serious adverse effect (AE), and incidence rate and severity of AEs that are definitely, probably, or possibly related to LP DBS throughout the study duration.
- 2) *Feasibility* measured as recruitment rate and completion rates of follow-up visits and assessments throughout the study duration.

The primary outcomes will be assessed continuously throughout the study.

H1. LP DBS for severe AUD will be deemed safe and well-tolerated by DSMB.

H1.a. LP DBS for severe AUD will not result in any serious adverse effects.

H1.b. The incidence rate of AE will be similar to standard of care DBS per the DSMB judgement.

H2. LP DBS for severe AUD will be deemed feasible.

H2.a. We will successfully recruit 3 participants for the study.

H2.b. Participants will complete >80% of all study follow-up visits and assessments.

Safety, tolerability, and feasibility will be assessed continuously throughout the study. We will screen for AEs using 4 approaches: 1) patient self-report, 2) clinical evaluations (medical, neurologic, and psychiatric), 3) questionnaires (e.g., screening for depression, suicidality, anxiety, apathy, mania) and 4) neuropsychological evaluation to screen for any LP DBS effects on various cognitive domains. Every AE will be evaluated for severity, expectedness and relatedness, and reported to the DSMB.

Safety and tolerability: The study will be deemed safe and tolerable if no serious AE that are definitely, probably, or possibly related to LP DBS occur during the study and if the AE severity and rate are not higher than standard of care DBS per DSMB's assessment.

Feasibility: the study will be deemed feasible if we successfully recruit the proposed number of participants and if participants complete >80% of all study follow-up visits and assessments.

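### Appendix A appears to give the mania, anxiety and apathy scales only at baseline, 6 and 12 months, although 7.4, 7.5 and 12.3 present them as adverse-event screening during follow-up

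*Protocol*

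**What the plan says.** Protocol 12.3, repeated in SAP 12.3, makes the incidence and severity of related adverse events a primary outcome and lists four ways of screening for them. The third is "questionnaires (e.g., screening for depression, suicidality, anxiety, apathy, mania"). The same section says "Safety, tolerability, and feasibility will be assessed continuously throughout the study". Protocol 3.3 also lists questionnaires for depression, anxiety, apathy and mania, and adds "These outcomes will be monitored throughout the entirety of the study".

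Protocol 7.4 groups the MADRS, Mini-MASQ, HARS, AES and YMRS as instruments meant to pick up adverse effects of DBS on mood and anxiety. Of the YMRS it says "this is an 11-item scale to screen for manic or hypomanic symptoms". It gives a frequency for the MADRS (weekly by phone, monthly in person) but none for the HARS, AES or YMRS.

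Protocol 7.5 says "the safety and efficacy assessments during follow-up visits are the same as what is listed in section 7.4". On frequency it says "Participants will be evaluated biweekly then monthly for the duration of the study (12 months"), and it refers the reader to Appendix A for the schedule.

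In Appendix A the rows for the HARS, AES and YMRS have three marks each. The C-SSRS row has six.

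**The concern.** The narrative sections present the mania, anxiety and apathy scales as safety instruments used during follow-up. The schedule that sites will work from appears to give them at none of the follow-up visits between assessments.

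The timing matters because of the risks the protocol itself names. Section 8.1 says "Risks associated with DBS titration/optimization include delirium, nausea, memory problems, seizures, mood disorder, mania", and goes on to list hyperactivity, euphoria and behavioural change. Section 6.1 allows further titration at follow-up visits. The scale aimed at one of the named titration risks would therefore be absent during the months when settings may still be changing.

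Two judgements depend on what is recorded in that period. Under 12.3 the DSMB compares adverse-event rate and severity with standard-of-care DBS. Under 13.5 it reviews safety once all three participants have completed the 6-month assessment. A safety statement covering mania, anxiety or apathy should be clear about how often those effects were actually rated.

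**Working it through.** **Inputs from Appendix A**
- Optimisation and switch-on: Days 50-51, window ±10.
- Follow-up visits 9 to 14: Days 65, 80, 110, 140, 170 and 200, window ±7. That is six visits.
- 6-month assessment: first day is Day 230, window ±7; further days are printed as Day 233, window ±5.
- Follow-up visits 18 to 22: five visits.
- First day of the 12-month assessment: Day 412.
- Marks per row: YMRS 3, HARS 3, AES 3, C-SSRS 6.

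**Step 1: where the three marks fall.** The columns are broken, so position has to be inferred. The YMRS, HARS and AES marks sit in the same three positions as those of the Trail Making Test and the Delay Discounting task. Section 13.4 places neuropsychological testing at baseline, 6 and 12 months, and 12.6 places the behavioural tasks at the same three times. The three marks are therefore read as baseline, 6 and 12 months. The C-SSRS row has 6 − 3 = 3 more marks, which fits use in the follow-up phases as well; that placement is also inferred.

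**Step 2: interval from switch-on to the first of these scales.**
- Nominal: 230 − 51 = 179 days; 230 − 50 = 180 days; if done on Day 233, 233 − 50 = 183 days.
- Shortest with windows: (230 − 7) − (51 + 10) = 223 − 61 = 162 days.
- Longest with windows: (233 + 5) − (50 − 10) = 238 − 40 = 198 days.

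Visits 9 to 14, six in all, fall inside this interval.

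**Step 3: the next interval.** From the 6-month to the 12-month assessment: 412 − 230 = 182 days, with visits 18 to 22 inside it.

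**Step 4: what the 6-month DSMB review would hold.** One YMRS after switch-on per participant, so 3 × 1 = 3 in the whole trial.

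**Step 5: what else is in place between switch-on and 6 months.**

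| Safeguard | Where | Mania rating scale? |
|---|---|---|
| MADRS weekly by phone, with escalation triggers | 7.4, Appendix A | No (depression) |
| C-SSRS | Appendix A | No (suicidality) |
| Psychiatric evaluation with CIWA and mental status examination | 7.4 | No |
| Phone checks 3-7 times per week until the 2-week visit | 9.1 | No |
| Adverse-event assessment at regular intervals | 10 | No |
| Collateral contacts; nurse available 24 hours | 5.2, 13.4 | No |

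**Step 6: cost of adding the YMRS.** Follow-up visits: 6 + 5 = 11. At about 5 minutes each (7.4), 11 × 5 = 55 minutes per participant. For comparison, the AES at 10-20 minutes would take 11 × 10 = 110 to 11 × 20 = 220 minutes.

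**The case against.** The strongest reply is that the text promises less than it seems to. A reader might infer from 7.5 that every scale is due at every follow-up visit. Section 7.5 does not say so. The 7.4 list includes one-off items such as the initial SCID, the ECG and the CT scans, so it cannot apply whole to each visit, and 7.5 itself points to Appendix A. Likewise, 12.3 describes the safety programme as continuous, not each instrument; neuropsychological evaluation is another of the four approaches and is done only at baseline, 6 and 12 months. Both points stand. What remains is narrower: scales described as adverse-effect screens appear at no interim follow-up visit, and no sentence in 3.3, 7.5 or 12.3 tells the reader so.

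A reader might also infer that psychiatric monitoring lapses for six months. It does not, as the table of safeguards shows. The gap is confined to the mania, anxiety and apathy scales (the Mini-MASQ row has the same pattern).

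A third tempting inference is that related adverse events will be undercounted, tilting the comparison in favour of LP DBS. The documents do not establish that. Clinical examination, self-report or collateral report may find the same events. Nothing says how mania, anxiety or apathy were ascertained in the standard-DBS rates, so denser rating here could instead raise this trial's count relative to the comparator. No scale score is itself an endpoint. A detection probability would need an assumed episode length and onset pattern, neither of which the documents give, so none is offered.

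Finally, mark counts in this table do not always agree with the text. FDG-PET shows four marks against three planned scans. Cue Reactivity and Card Guessing lack a mark where 12.6 implies a 12-month assessment. The adverse-events row shows only three marks although section 10 requires regular assessment. This is a fair reason for caution about placement. It is offset by the exact match between the three scale rows and the Trail Making and Delay Discounting rows, whose timing the text confirms.

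**Conclusion.** The point holds in limited form. If Appendix A means what it appears to mean, the first mania, anxiety or apathy scale after switch-on comes 179 to 183 days later on nominal dates (162 to 198 with windows), after six follow-up visits at which settings may be changed. A second interval of 182 days follows.

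This rests on the inferred column placement, which the sponsor can confirm at once from the source table. It also rests on reading 7.4, 7.5 and 12.3 together as presenting these scales as follow-up safety screening. It is a mismatch between sections and a cheap opportunity to improve ascertainment of a primary safety outcome. It does not show that safety monitoring is absent or that the adverse-event comparison is biased in a known direction. The YMRS is the most useful of the three to add, because mania is a named titration risk, no other planned follow-up instrument rates it, and the scale is short.

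**What to change.** Reconcile 3.3, 7.5, 12.3 (Protocol and SAP) and Appendix A.

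- **Preferred:** in Appendix A, add the YMRS at the existing follow-up visits where the C-SSRS is already given, about 11 visits. This changes one row and adds roughly one hour per participant in total, with no new visits. The downside is slightly longer visits, and the added ratings would enter the assessment-completion count in 12.3.
- **Optional:** add the HARS and AES at the same visits if burden allows. The AES alone would take about 2 to 4 hours per participant, and 7.4 gives no duration for the HARS, so leaving them at the sparser schedule is reasonable if the text says so.
- **If the sparse schedule is kept:** state in 3.3, 7.5 and 12.3 that mania, anxiety and apathy are rated by scale only at baseline, 6 and 12 months, and carry that limit into the safety conclusion and the DSMB's 6-month review. This costs only a wording change.

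In either case, 7.4 should give a frequency for the YMRS, HARS and AES, as it does for the MADRS.

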7.6 End of Study Safety and Efficacy Assessments/Procedures

If explanted, the patient will be monitored during the 24-hours post-surgery and will be assessed by post-op CT scan. A follow-up visit with the neurology/neurosurgery team will be scheduled 2 weeks later to ensure safety. They will then be referred to outpatient psychiatry clinic for standard of care follow-ups. Should the study team and the patient agree to leave the DBS system implanted, then the patient will be followed yearly for the next 5 years, possibly longer. These follow ups will involve standard of care clinical evaluations in the Neurology and Psychiatry clinics of the study investigators ([name] for Neurology and [name] for psychiatry). During these visits, we will continue to screen for potential adverse effects, conduct neurological and psychiatric evaluations, including assessing their alcohol use.

7.7 Early Discontinuation Safety Assessments

Similarly to end-of-study, participants who are withdrawn from the study early will undergo explantation surgery of the DBS system. Again, these patients will be monitored overnight after surgery, and will receive a post-operative CT scan to ensure there are no complications. A follow-up visit with the neurology/neurosurgery team will be scheduled 2 weeks later to ensure safety. They will have 3 monthly follow-up visits after DBS explantation. They will then be referred to outpatient psychiatry clinic for standard of care follow-ups.

8 Potential Risks and Benefits

8.1 Reasonably Foreseeable Risks Related to Study Device

More than 208,000 DBS systems have been implanted thus far, the majority for fully FDA-approved indications, including PD, epilepsy, and essential tremor, or for Humanitarian Device Exemption indications, including obsessive compulsive disorder (OCD) and dystonia. The safety profile of DBS continues to improve, however there remains a certain level of risk to patients. In a systematic review of 52 DBS studies, including 2249 patients total, between 2008 and 2020, the overall complication rate was 16.7% (375/2249). These complications spanned different categories and a range of severities: systemic (0.9%), intracranial (2.7%), neurologic (4.6%), hardware (2.2%), and incisional (3.4%)[154]. A similar study included 96 DBS studies, including 8983 patients, investigated hardware-related complications. These included infections (5.1%), lead migration (1.6%), lead fracture (1.5%), lead failure (0.7%), neurostimulator malfunction (1.1%), and skin erosions (0.5%) [155]. No deaths were reported in either

systematic review. The risk of intracranial hemorrhage is likely higher in patients with alcohol use disorder and alcoholic liver disease due to the effects of liver disease and alcohol on platelets and other bleeding factors. Severe intracranial hemorrhage can be fatal in this patient population.

From the device brochure, Medtronic DBS therapy has a risk of adverse events related to the therapy, device, or procedure. These include: "intracranial hemorrhage, cerebral infarction, CSF leak, pneumocephalus, seizures, surgical site complications (including pain, infection, dehiscence, erosion, seroma, and hematoma), meningitis, encephalitis, brain abscess, cerebral edema, aseptic cyst formation, device complications (including lead fracture and device migration) that may require revision or explant, extension fibrosis (tightening or bowstringing), new or exacerbation of neurological symptoms (including vision disorders, speech and swallowing disorders, motor coordination and balance disorders, sensory disturbances, cognitive impairment, and sleep disorders), psychiatric and behavioral disorders (including psychosis and abnormal thinking), cough, shocking or jolting sensation, ineffective therapy, and weight gain or loss."

DBS Explantation risks: these include hemorrhage and infection but these risks are much lower than during implantation surgery (the risk of infection is low without implanted hardware and the hemorrhage risk is associated with lead insertion, not removal). There is also the possibility of emotional letdown feeling by participants whose DBS was not effective and will be explanted.

Risks associated with DBS titration/optimization include delirium, nausea, memory problems, seizures, mood disorder, mania, hallucinations, suicidal ideation, muscle weakness, shocking sensation, numbness, paresthesias, facial flushing, motor contraction, dizziness, headaches, pain, changes in vital signs, hyperactivity, euphoria, dry mouth, itching, insomnia, fatigue, restlessness, weight gain or loss, speech difficulties, blurred or double vision, unusual smell and taste sensations, and behavioral changes. In addition, it is possible that alcohol use will worsen with DBS stimulation. Specific risks associated with anteromedial GPi DBS targeting include tetanic contraction (posterior limb of internal capsule), photopsia (optic tract), behavioral changes (anterior limb of internal capsule), and behavioral and cognitive changes (substantia innominata).

A review of LP DBS in Tourette's patients [39] reported 7 cases of stimulation-induced side effects that included lethargy, nausea, and paresthesias. However, all these symptoms are reversible with adjustment of stimulation parameters [39].

The device brochure also includes additional warnings about device interactions and precautions (see appendix B).

8.2 Reasonably Foreseeable Risks Related to Research Interventions

- **Loss of confidentiality:** This is associated with any of the study encounters
- **Electrocardiogram:** The participant may experience some skin irritation from the location of ECG leads.
- **Blood tests:** The participant may experience some discomfort at the site of needle entry, and there is a risk of a "black-and-blue" mark. There is a remote risk of fainting or local infection. Blood tests may reveal incidental findings.
- **Liver ultrasound:** The participant may experience some discomfort from the pressure of the ultrasound probe on his/her abdomen.

- **Detox:** While undergoing detox the participant can experience alcohol withdrawal and may experience restlessness, sweating, loss of appetite, nausea, vomiting, agitation, irritability, anxiety, fast heart rate, tremor, disorientation, headache, insomnia, and seizures.
- **MRI scans with contrast:** (The below risks will be lessened by exclusion of participants with predetermined MRI contraindications - see exclusion criteria)
 - The MR-magnet may cause injury in subjects who have pacemakers or other implanted electrical devices, some types of dental implants, aneurysm clips (metal clips on the wall of a large artery), metallic prostheses (including metal pins and rods, heart valves, and cochlear implants), permanent eyeliner, implanted delivery pump, or shrapnel fragments. Welders and metal workers are also at risk for injury because of possible small metal fragments in the eye of which they may be unaware.
 - Gadolinium contrast used with MRI scans is associated with very low risk of rare vision problem in fetuses.
 - People with fear of confined spaces (claustrophobia) may become anxious during an MR-imaging.
 - People with back problems may have back pain or discomfort from lying in the scanner.
 - The noise from the scanner is loud enough to damage hearing, especially in people who already have hearing loss.
 - The risks of an IV catheter (for contrast injection) include bleeding, infection, or inflammation of the skin and veins with pain and swelling. Symptoms from the contrast infusion are usually mild and may include coldness in the arm during the injection, a metallic taste, headache, and nausea. In an extremely small number of patients, more severe symptoms have been reported including shortness of breath, wheezing, hives, and lowering of blood pressure. People with kidney disease are at risk for a serious reaction to gadolinium contrast called "nephrogenic systemic fibrosis" which has resulted in a very small number of deaths.
 - MRI scans may reveal incidental findings.
- **PET scans (FDG) & CT head scans:**
 - Radiation: This proposal involves exposure to radiation from $[^{18}\text{F}]$ FDG-PET scans, and CT scans. If subjects need to be screened for metal prior to MRI, they will receive an x-ray which could also be an additional source of radiation exposure. Participants will receive 3 radioactive injections ($[^{18}\text{F}]$ FDG) over a period of 8 months, 3 low dose head CT scans for attenuation correction, and 3 regular head CT scans (over 13 months) for surgical planning and surgical care. The 12-month level of radiation exposure is therefore lower than the radiation dose exposure limit for RDRC studies. The maximum injected dose for each $[^{18}\text{F}]$ FDG scan will not exceed 5 mCi. An individual subject who participates in the study will receive no more than 15 mCi of $[^{18}\text{F}]$ FDG (5 mCi/scan) in a 12-month period. This will amount to a total radiation exposure equivalent to a uniform whole-body dose of 1.056 rem (0.352 rem * $[^{18}\text{F}]$ FDG scan x 3 time points). The total radiation dose exposure from 3 low dose CT scans will be 0.048 (0.016/scan). The radiation dose from 2 regular head CT scans (only 2 regular CT scans in 12 months) will be 0.32 rem (0.16 rem/scan). Thus, the cumulative exposure from PET and CT scans is 1.424 rem. This is ~ 28% of the annual whole-body radiation exposure (5 rem) permitted to radiation workers by federal guidelines.

The organ that will receive the largest absorbed radiation dose based on human dosimetry studies is the urinary bladder wall (7.2 rem for 15 mCi) for $[^{18}\text{F}]$ FDG. As the dose-limiting critical organ for the protocol is the urinary bladder wall, the maximum

exposure to this organ will need to be limited to 15 rem/study. AUD subjects who complete all 3 PET scans will receive a total radiation dose-exposure-equivalent to the urinary bladder of 7.2 rem in a 12-month period. The proposed dose exposures are less than the single study annual limit for both whole-body (5 rem) and dose-limiting critical organ (15 rem) under proposed guidelines for RDRC studies.

This radiation dose is not expected to produce any harmful effects, although there is assumed to be no minimum level of radiation exposure for non-radiation workers considered to be totally free of the risk of causing genetic defects or cancer. The risk associated with the amount of radiation exposure participants receive in this study is considered relatively low and acceptable.

Radiation from CT and PET scans can be harmful to a developing fetus. No PET studies will be performed on pregnant or potentially pregnant women, as confirmed by urine pregnancy testing prior to FDG/PET scan. [18F]FDG is FDA approved for human use in PET imaging for assessment of abnormal glucose metabolism for numerous clinical indications. Its use in this protocol is off-label but considered to be generally safe and effective as approved by the University of Pittsburgh's Radioactive Drug Research Committee and IRB. [F-18] labeled PET radiotracer has a half-life of 110 minutes and is not considered to be a biohazard.

For reference, the average person in the United States receives a radiation exposure of 0.3 rem per year from natural sources, such as the sun, outer space, and the earth's air and soil.

- **Pharmacology:** The mass dose for [¹⁸F]FDG used in these studies is negligible and is not associated with any pharmacological effects. However, as with any drug, the possibility of idiosyncratic reaction exists and will be mentioned in the consent forms. A physician is present at the PET facility. If adverse effects occur that require medical intervention, UPMC will administer it.
- **Fasting before PET scans or liver US:** This may cause feelings of hunger and in some subjects hypoglycemia.
- **Female contraception:** Side effects depend on the participant and the type of contraception method used. Symptoms span a wide variety, including nausea, headache, spotting between periods, breast tenderness, and mood changes.
- **Questionnaires:** The risks of AUD, mood and anxiety, sleep, and impulsivity assessments include discomfort from the nature of the questions or discomfort from the length of time required to complete the questionnaires. Specifically, questions related to thoughts of suicide or self-harm may trigger emotions that put the participant at greater risk.
- **Neuropsychological evaluation:** The risks of this assessment include discomfort from the nature of the questions or discomfort from the length of time required to complete the assessment.
- **Cognitive and behavioral tasks:** The risks of these tasks include discomfort from the nature of the tasks or discomfort from the length of time required to complete the tasks. Exposure to alcohol cues could cause craving, anxiety and discomfort. **Electroencephalogram:** The participant may experience some discomfort and some scalp/skin irritation from the location of EEG leads.
- **Financial risks during study:** All the costs of the study procedures and interventions will be covered by the study funding agency. However, participating in the study could incur financial burden on the participants in terms of lost productivity during study visit evaluations and interventions, travel and parking costs, and food costs.

- **Financial risks after study completion:** If DBS was not efficacious, it will be explanted and there will be no financial risks after study completion. However, if DBS was efficacious and the participant chooses to keep the DBS system implanted beyond the study period, there will be financial risks due to:
 - 1) The need for yearly follow-ups for up to 5 years and possibly longer in neurology and psychiatry clinics for standard of care assessments as well as screening for delayed adverse events. This cost will not be covered by the study.
 - 2) The need to replace the battery of the neurostimulator when depleted (after several years). This cost will not be covered by the study.
 - 3) If a participant initially chooses to keep the DBS system implanted but decides to have it electively explanted later, after the study has ended. This cost will not be covered by the study.

